6.3. Clinical Research Unit (CRU) Check-in (All Parts, Day -1)

Subjects will arrive at the CRU at approximately 11 am (Parts A, B, C, and D Extension) or sometime in the morning (Parts D and E [approximately 24 hours before the first dose]) on the day before the scheduled first dose of study drug. The following procedures will be done:

- For Part D Extension subjects who did not have a Part D Extension screening visit only, obtain signed informed consent from the subject and from the subject's caregiver/LAR (if applicable)
- Review of inclusion/exclusion criteria
- Obtain updates, if any, for medical history
- Perform physical examination including weight
- Measure vital signs
- Conduct 12-lead ECG
- Collect fasting blood sample(s) for clinical laboratory testing (hematology, coagulation and biochemistry); and, for female subjects of childbearing potential only, serum pregnancy test (pregnancy test must be negative for the subject to receive study drug)
 - Hematology, coagulation and biochemistry laboratory tests do not need to be repeated if they were already assessed at the pre-screening or screening visit that took place within 60 days prior the first day of dosing on Day 1
- Collect fasting urine sample for urinalysis, drugs of abuse screen (also cotinine screen for subjects in Parts A, B, and C only) and for the following urinary markers of renal function: UPCR and UACR
 - Urinalysis, UPCR and UACR do not need to be repeated if they were already assessed at the pre-screening or screening visit that took place within 60 days prior the first day of dosing on Day 1
- Collect AE and concomitant medication data
- Feed the subject (2 meals [lunch and dinner])
- Fast the subject overnight for at least 10 hours

For Parts D and E only, the following procedures will be done in addition to the ones listed above:

- Collect blood sample for analysis of biomarkers of galactose metabolism including galactose, galactitol, and galactose-1-p
- Collect urine over 24 hours (morning of Day -1 to immediately before the first dose [Day 1]) for analysis of galactitol (an aliquot of the total urine collected will be analyzed for creatinine)
- Feed the subject (2 to 3 meals depending on check-in time)

Subjects who no longer fulfill all inclusion criteria and/or now fulfill one or more exclusion criteria will be discontinued from the study and sent home. These subjects will be replaced.

Subjects who continue to fulfill all inclusion criteria and none of the exclusion criteria will continue in the study.

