6.1. Prescreening Period (De novo Part D Extension Subjects Only)

Prescreening can be done at any time during a home health visit (in-clinic visit also permitted). The purpose of prescreening is to identify subjects who may be interested in and qualify for the study. A prescreening ICF must be completed before any study-specific prescreening procedure is conducted.

Prescreening is optional. Some subjects may do the prescreening activities as part of screening.

Prescreening activities may include the following:

- Collect blood sample for assessment of GALT activity in RBCs and GALT gene analysis
- Collect urine sample (spot collection) for analysis of galactitol
- Collect fasting blood sample(s) for clinical laboratory testing (hematology, coagulation, and chemistry) and serology testing (screening for HIV, hepatitis B, and hepatitis C)
- Measure body weight
- Measure height
- Obtainment of medical history only for documented diagnosis of Galactosemia, if available

6.2. Screening Period (Days -28 through -1 for Parts A, B, and C and Days -40 through -1 for Parts D and E, and Days -60 through -1 for Part D Extension)

The screening visit must occur within 28 days before the first dose of study drug for Parts A, B, and C; within 40 days before the first dose of study drug for Parts D and E; and within 60 days before the first dose of study drug for Part D Extension.

The Part D Extension screening visit is only applicable to the following subjects:

- De novo subjects
- Subjects whose last visit in Part D was >60 days before Day 1 in Part D Extension

Part D Extension subjects who previously participated in Part D and had a last Part D visit within 60 days before Day 1 of the extension do not need a screening visit for the extension.

Subjects will be evaluated at the screening visit to determine their eligibility to enroll in the study. The following procedures will be done at screening (home health visit or in-clinic visit):

- Obtain signed informed consent from the subject and from the subject's caregiver/LAR (if applicable)
The informed consent documents will be discussed with each potential subject and caregiver/LAR (if applicable), and each potential subject (and caregiver/LAR if applicable) will sign the informed consent form(s), as appropriate, for the study prior to any study-specific procedures being performed.
- Review inclusion/exclusion criteria
- Obtain medical history (including current medication)

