- Obtain demographic data (not necessary for Part D subjects being re-screened for Part D Extension)

- Perform physical examination including height (unless already taken at prescreening) and weight
- Measure vital signs
- Conduct 12-lead ECG
- Collect fasting blood sample(s) for clinical laboratory testing (hematology, coagulation and biochemistry); serology testing (screening for HIV, hepatitis B, and hepatitis C); and, for female subjects of childbearing potential only, serum pregnancy test (also FSH test for female subjects claiming postmenopausal status) (Note: The clinical laboratory testing and serology testing do not need to be repeated if already done at prescreening and prescreening was within 60 days before the first dose of study drug in Part D Extension.)
- Collect fasting urine sample for urinalysis, drugs of abuse screen (also cotinine screen for subjects in Parts A, B, and C only), and for the following urinary markers of renal function: Urine protein-to-creatinine ratio (UPCR), urine albumin-to- creatinine ratio (UACR).

For Parts D, E, and D Extension only, the following procedures will be done in addition to the ones listed above:

- Collect blood sample for assessment of GALT or GALK activity in red blood cells and GALT or GALK gene analysis (GALT for Parts D and D Extension and GALK for Part E) (if not already done during prescreening)
- Collect blood sample for assessment of aldose reductase activity
- Collect blood sample for analysis of biomarkers of galactose metabolism including galactose, galactitol, and galactose-1-p
- Collect urine sample (spot collection) for analysis of galactitol (if not already done during prescreening)

Note: For Part D Extension subjects who were previously screened for Part D but had the last Part D visit >60 days before Day 1 in the extension, GALT and aldose reductase activity assessments do not need to be repeated.

Subjects who are taking any disallowed medication(s) (see [Section 4.1.2](#), [Section 4.2.2](#), and [Section 4.6](#)) but otherwise eligible for the study may washout their disallowed medications (washout of at least 5 half-lives of the disallowed medication with the longest half-life). After the washout period, they may be rescreened.

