

**APPENDIX A. SCHEDULE OF ASSESSMENTS FOR PART A (SAD IN
HEALTHY SUBJECTS)**

Schedule of Assessments for SAD in Healthy Subjects (Part A)

PROCEDURE	Screening (Days -28 to -1)	Day -1 ^a (Check-in)	Day 1	Day 2	Day 3 ^a (Check-out)	Day 4 ^a (Check-out)	EOS Visit ^b (Day 28±2)
Check-in		X ^a					
Discharge					X ^a	X ^a	
Informed consent	X						
I/E criteria	X	X					
Medical history/updates	X	X					X
Demographic data	X						
Physical examination ^c	X	X			X		X
Vital signs ^d	X	X	X	X	X		X
Electrocardiogram ^e	X	X	X		X		X
Clinical laboratory testing (biochemistry, hematology, coagulation, urinalysis, UACR, UPCR) ^f	X	X			X		X
HIV and hepatitis B & C testing	X						
Urine drug/cotinine screen	X	X					
Pregnancy test (female subjects) ^g	X	X			X		X
Drug administration			X				
Blood sample collection for PK analysis ^h			X	X	X		
Urine collection for PK analysis ⁱ (Cohorts A4 and A5 only) ^j			X	X	X	X	
Adverse Events							Throughout Study
Prior/Concomitant medications	X						Throughout Study

EOS = end-of-study; FSH = follicle-stimulating hormone; HIV = human immunodeficiency virus; I/E = inclusion/exclusion; PK = pharmacokinetic;

SAD = single ascending dose; UACR – urinary albumin to creatinine ratio; UPCR = urinary protein to creatinine ratio

a: Check-in will occur around 11 am on Day -1. For Cohorts A1, A2, and A3, discharge from the clinic will occur on Day 3 after all Day 3 procedures are done and blood samples for PK are collected through 48 hours after the dose. For Cohorts A4 and A5, discharge from the clinic will occur on Day 4 after urine for PK is collected through 72 hours after the dose.

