Clinical laboratory testing (biochemistry, hematology, coagulation, urinalysis) ^f	X	X				X				X
HIV and hepatitis B & C testing	X									
Urine drug/cotinine screen	X	X								
Pregnancy test (female subjects) ^g	X	X				X				X
Drug administration ^h			X	X	X	X	X			
Blood sample collection for PK analysis ⁱ			X	X				X	X	
Adverse events									Throughout Study	
Prior/Concomitant medications	X								Throughout Study	

CSF = cerebrospinal fluid; EOS = end-of-study; FSH = follicle-stimulating hormone; HIV = human immunodeficiency virus; I/E = inclusion/exclusion; MAD = multiple ascending dose; PK = pharmacokinetic; QD = once daily.

a: Check-in will occur around 11 am on Day -1 and Discharge will occur on Day 9 after the blood sample for PK is collected at 48 hours after the Day 7 dose and all Day 9 procedures are done.

b: The EOS visit will be scheduled for 28 (±2) days after the last dose of study drug.

c: All physical examinations will include weight; however, height will be measured only at screening.

- d: Vital signs will be measured at Screening, check-in on Days -1 and 6, predose (within 60 min before the dose) on Days 1 and 7, at 4 hours (± 10 minutes) after the dose on Days 1 and 7, once daily on Days 2, 8, and 9, and at the EOS visit.
- e: Electrocardiograms will be performed at Screening, Day -1 check-in, predose (within 60 min before the dose) on Days 1 and 7, at 2 hours (± 10 minutes) after the dose on Days 1 and 7, and at the EOS visit.
- f: Samples for clinical safety laboratory tests will be collected under fasting conditions.
- g: Serum pregnancy tests at Screening, Day -1, and EOS visits; urine pregnancy tests at other time points. Also, female subjects claiming postmenopausal status will have that status verified with an FSH test at Screening. Once a female subject is verified as postmenopausal or otherwise not of childbearing potential, the subject is exempt for further pregnancy tests. On Day 6, the urine pregnancy test must be done (and the result negative) before study drug is administered.
- h: All doses of study drug will be administered at the clinic.

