- a: Subjects will arrive at the CRU in the morning on Day -1 (approximately 24 hours before the planned first dose). For the Days 12, 20, and 32 check-ins/visits, the subject should arrive after an overnight fast of at least 10 hours (and before breaking the fast) and before taking study drug. On Days 6 and 60, the subject should not have any study drug in his/her possession and should arrive (in a fasted condition) in the morning (before the planned time of study drug dosing to be given in the clinic on Day 6 [no study drug dosing on Day 60]).
- b: Discharge from the 1st, 2nd, and 3rd (last) in-clinic periods of the required portions of Part D will occur on Days 3 (Cohorts D1 and D2) or 4 (Cohort D3), 13, and 34, respectively, after all procedures for that day are done and the last blood sample or urine collection for that in-clinic period is collected.
- c: The EOS visit will be scheduled for 28 (±2) days after the last dose of study drug in the MAD portion.
- d: All physical examinations will include weight; however, height will be measured only at screening.
- e: Vital signs will be measured at Screening, every check-in, every check-out, predose (within 60 min before the dose) and 4 hours (±10 minutes) after the dose on Days 1, 6, 12, 20, and 32; once daily on all other in-clinic days; and at the EOS visit.
- f: Electrocardiograms will be performed at Screening, Day -1 check-in, predose (within 60 min before the dose) and 2 hours (±10 minutes) after the dose on Days 1, 6, 12, 20, and 32 and at the EOS visit.
- g: Samples for clinical safety laboratory tests (hematology, chemistry, coagulation, and urinalysis) will be collected under fasting conditions.
- h: Serum pregnancy tests at Screening, Day -1, and EOS visits; urine pregnancy tests at other time points. Also, female subjects claiming postmenopausal status will have that status verified with an FSH test at Screening. Once a female subject is verified as postmenopausal or otherwise not of childbearing potential, the subject is exempt for further pregnancy tests. On Days 6, 12, 20, and 32, the urine pregnancy test must be done (and the result negative) before study drug is administered.

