- p: Urine for galactitol measurement will be collected over the 24 hours immediately before and the 24 hours immediately after the dose on Day 1. Urine for galactitol measurement will be collected over the 24 hours immediately after the dose on Days 12 and 32 during the MAD period. For each 24-hour collection of urine for galactitol measurement, an aliquot of the total urine collected will be analyzed for creatinine. Also, a spot collection for urine galactitol measurement will be taken at screening.
- q: Visit window \pm 1 day of scheduled visit for all visits except the EOS visit which has a window of \pm 2 days.
- r: These assessments must be performed on Day -1 even if they were already performed earlier during the screening period.

**APPENDIX E. SCHEDULE OF ASSESSMENTS FOR PART E (SAD AND
MAD IN SUBJECTS WITH GALK-DEFICIENT
GALACTOSEMIA)**

Schedule of Assessments for SAD and MAD in Subjects with GALK-deficient Galactosemia (PART E)^o

PROCEDURE	Screening (Days -40 to -1 ^a)	Day 1	Day 2	Day 3 ^b	Day 5	Day 6 ^a	Day 12 ^a	Day 13 ^b	Day 20 ^a	Day 32 ^a	Day 33	Day 34 ^b	Day 60 (±2)	EOS Visit ^c Day 60 (±2)
Check-in	X ^a (Day -1)						X ^a			X ^a				
Discharge				X ^b				X ^b					X ^b	
Informed consent	X													
I/E criteria	X ^p													
Medical history/updates	X ^p													X
Demographic data	X													
Physical examination ^d	X ^p					X	X		X	X			X	X
Vital signs ^e	X ^p	X	X	X		X	X	X	X	X	X	X	X	X
Electrocardiogram ^f	X ^p	X				X	X		X	X				X
Clinical laboratory testing ^g	X ^p					X	X		X	X				X
GALK activity in red blood cells and GALK gene analysis	X													
Aldose Reductase activity	X													
HIV and hepatitis B & C testing	X													
Urine drug screen	X ^p													
Pregnancy test (female subjects) ^h	X ^p					X	X		X	X				X
Drug administration ^j		X												
5-day washout ^k				X										
Blood sample collection for PK analysis ^l		X	X	X			X	X		X	X	X		
Blood sample collection ^m for galactose, galactitol, galactose-1-p and other galactose metabolites	X ^p	X	X	X			X	X		X	X	X		

PROCEDURE	Screening (Days -40 to -1 ^a)	Day 1	Day 2	Day 3 ^b	Day 5	Day 6 ^a	Day 12 ^a	Day 13 ^b	Day 20 ^a	Day 32 ^a	Day 33	Day 34 ^b	Day 60 (±2)	EOS Visit ^c
Urine sample collection ⁿ for galactitol	X ^p	X	X				X	X		X	X			
Adverse events														Throughout Study
Prior/Concomitant medications	X ^p													Throughout Study

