- j: Samples for clinical safety laboratory tests (hematology, chemistry, coagulation, urinalysis, UACR and UPCR) will be collected under fasting conditions. At the Screening visit only (i.e., only applicable to subjects for whom this visit is required and does not need to be repeated at screening if already done at prescreening), HIV and hepatitis B & C testing will also be done. Hematology, chemistry, and coagulation at the Screening visit (i.e., only applicable to subjects for whom this visit is required) does not need to be repeated if already done at prescreening and prescreening was within 60 days before the first dose of Part D Extension study drug. Clinical safety laboratory tests (hematology, chemistry, coagulation, urinalysis, UACR and UPCR) do not need to be repeated at Day -1 if already done at prescreening or screening and the prescreening/screening visit was done within 60 days before the first dose of Part D Extension study drug.
- k: Serum pregnancy tests will be done at Screening (if applicable), Day -1 (also urine test if serum test cannot be processed immediately), and EOE visits; urine pregnancy tests will be done at all other time points. From Days 1 through 90, pregnancy tests must be done (and the result negative) on dosing days before study drug is administered. A pregnancy test must be performed on Day -1 even if already performed earlier during the screening period.
- m: On Days 1, 2, and 90, study drug will be administered at the clinic. On Days 30 and 60, study drug will be administered during the visit (home health or in-clinic). All other doses of study drug will be taken at home QD with water in the morning (preferably after an overnight fast of ≥ 10 hours with the fast broken ≥ 2 hours after the dose). Study drug administration should be at approximately the same time of day (preferably 8 am) throughout the extension. Drug accountability (including dispensing and/or collecting) will be assessed at all visits during the 90 days of dosing.
- n: On Day 1, a predose (within 60 minutes before the dose) blood sample for PK will be collected. On Days 30, 60, and 90, blood samples for PK will be collected predose (24 hours [± 15 minutes] after the dose taken the day before and within 60 minutes before the dose administered on that day) and at 2, 4, 8, and 12 hours (± 5 minutes for all time points) after the dose. An additional sample will be taken on Day 91 at 24 hour after the Day 90 dose.

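### The Day -1 laboratory waiver in Protocol Section 6.3 names no study part and so contradicts the Part D and Part E schedules; it should be limited to the Part D Extension

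*Protocol*

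**What the plan says.** Section 6.3 of the protocol applies by its title to every part. Under the Day -1 blood collection it states: "Hematology, coagulation and biochemistry laboratory tests do not need to be repeated if they were already assessed at the pre-screening or screening visit", with a 60-day limit counted back from Day 1. A parallel sub-bullet under the urine collection waives urinalysis, UPCR and UACR on the same terms.

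Section 6.2 sets the screening windows: "within 28 days before the first dose of study drug for Parts A, B, and C; within 40 days before the first dose" for Parts D and E, and 60 days for the Part D Extension.

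The schedules treat Day -1 differently from Section 6.3:

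- **Appendices D and E.** One column covers the whole screening period. The laboratory entry carries footnote r (Appendix D) or p (Appendix E), and both footnotes read "These assessments must be performed on Day -1 even if they were already performed earlier during the screening period". Footnote g of Appendix D defines the panel: "Samples for clinical safety laboratory tests (hematology, chemistry, coagulation, and urinalysis) will be collected under fasting conditions". Appendix E has the same footnote.
- **Appendix A.** The row "Clinical laboratory testing (biochemistry, hematology, coagulation, urinalysis, UACR, UPCR" is marked at Screening and again on Day -1. Its only laboratory footnote concerns fasting.
- **Appendices B and C.** The row "Clinical laboratory testing (biochemistry, hematology, coagulation, urinalysis" is marked the same way, again with no waiver.
- **Appendix F (Part D Extension).** Footnote j contains the Day -1 waiver, on condition that the earlier "visit was done within 60 days before the first dose of Part D Extension study drug".

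Section 6.2 has a similar note on not repeating prescreening tests at screening. It applies where "prescreening was within 60 days before the first dose of study drug in Part D Extension".

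**The concern.** For Parts D and E, one section says the tests may be skipped and the schedule says they must be done. A site cannot tell from the text which governs. For Parts A to C the conflict is milder: the schedules call for a Day -1 sample, but no footnote insists on repetition.

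No laboratory sample is scheduled on Day 1. If the Day -1 sample is skipped, the subject receives a first dose on screening values alone. Under Section 9.2.1, baseline then falls back to the last non-missing value before dosing, which is the screening value. That value feeds the change-from-baseline and shift tables for hematology, chemistry and coagulation (SAP 7.12.3). Safety is the primary endpoint.

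Day -1 is also an eligibility check. Section 6.3 has the criteria reviewed again and sends home anyone who no longer qualifies. Several exclusions that depend on laboratory data state no time point: hematopoietic and hepatic disease (4.2.2, criterion 1), renal function (criterion 4) and hematological disease (criterion 7). Without a Day -1 sample, that re-check has no current value to work from.

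**Working it through.** The plan gives no figure to reproduce. The check compares texts and does some arithmetic on windows and cohort sizes.

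**1. Does the 60-day condition limit the waiver in Parts A to E?**

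| Parts | Screening cap (6.2) | Margin to 60 days | Oldest possible baseline | Added age against Day -1 |
|---|---|---|---|---|
| A, B, C | 28 days | 60 − 28 = 32 | 28 days | 28 − 1 = 27 |
| D, E | 40 days | 60 − 40 = 20 | 40 days | 40 − 1 = 39 |

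Every subject screened within the window meets the condition, so it restricts nothing in these parts.

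**2. Can a limit by part be read into Section 6.3?** Other items there are limited explicitly: the consent step to certain Extension subjects, cotinine to Parts A to C, and the biomarker and 24-hour urine collections to Parts D and E. The two waiver bullets have no such limit, so the literal reading is all parts.

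**3. What was intended?** Four features point to the Part D Extension. Prescreening exists only for de novo Extension subjects (6.1). Sixty days is the Extension's screening window (6.2). The related note in 6.2 names the Extension. Appendix F footnote j gives the same Day -1 waiver and also names it.

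**4. Which tests conflict?** For hematology, chemistry, coagulation and urinalysis, Section 6.3 contradicts Appendices D and E and differs from A to C. UPCR and UACR are listed for Day -1 only in Appendix A, so among Parts A to E only that schedule differs from the waiver on them.

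**5. How many planned subjects could be affected?** The protocol's status text, written for version 5.0, describes Cohorts A1 to A5, B1 to B3, C1 to C2 and D1 to D2 as completed. The SAP follows protocol version 6.0, and its check-in list (SAP 3.1.2.2) has no waiver, which suggests the waiver was added later. I assume so.

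- Planned in Parts A to E (Table 1): 40 + 28 + 12 + 18 + 18 = 116
- Already past Day -1: A 40, B1 to B3 8 + 6 + 8 = 22, C1 to C2 4 + 4 = 8, D1 to D2 6 + 6 = 12; total 82
- Remaining: 116 − 82 = 34, made up of B4 6, C3 4, D3 6 and Part E up to 18
- With D3 and three Part E cohorts enlarged to 8: 6 + 4 + 8 + 24 = 42

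The lower bound is 0. Section 5.3 describes Parts D and E in the past tense, and no site need have used the waiver. Unplanned cohorts above 40 mg/kg are not counted.

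**The case against.** The strongest reply is that this is a dropped scope phrase whose intent is plain, and that sites are sent to the schedules anyway. Section 7.1.2 says laboratory samples follow the Schedules of Assessments, and Section 7 refers to their footnotes for time frames. The waiver is permissive, so a site that draws the Day -1 sample complies with both texts. The analyses are descriptive, the fallback baseline is prespecified, placebo subjects in Parts A, B, D and E fall under the same rule, and Parts D and E have a Day 6 sample before multiple dosing.

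Most of that stands and keeps the severity low. It does not remove the conflict. The pointers in 7 and 7.1.2 are not a rule of precedence that cancels an explicit waiver in Section 6, and I found no such rule. The Day 6 sample comes after the single dose, so it cannot serve as a pre-treatment value.

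Some stronger readings are tempting but not supported:

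- *Every subject in Parts A to E was exposed to the waiver.* The wording would cover them all, but the status text shows most planned cohorts already completed. On the assumed dating, the Part A difference over UPCR and UACR has no practical effect.
- *SAP 3.2.2 also contradicts Section 6.3.* It lists Day -1 without a waiver for the Part D Extension too, where the waiver is clearly intended. Since the SAP follows version 6.0, its silence shows only a version lag.
- *Laboratory eligibility as a whole is undermined.* The general laboratory criteria (4.1.1 inclusion 5; 4.1.2 exclusion 13) are judged at screening. Only exclusions without a stated time point are touched, and for renal function the Investigator has the final decision.
- *The eGFR trigger in Appendix H shifts as well.* Appendix H does not define its baseline, so this cannot be concluded.

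**Conclusion.** The point holds for the text. Section 6.3 directly contradicts Appendix D footnote r and Appendix E footnote p on hematology, chemistry, coagulation and urinalysis, and it differs from the Day -1 schedules in Appendices A to C. It is more than clerical, because as written it permits a first dose on safety laboratory values up to 28 days (Parts A to C) or 40 days (Parts D and E) old, and moves the laboratory baseline back by up to 27 or 39 days.

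The consequence is small: descriptive safety tables and part of the Day -1 eligibility re-check. Exposure among planned subjects is 0 to 34, or up to 42 with enlarged cohorts. That range rests on the waiver postdating the version 5.0 status text; the documents suggest this but do not state it. Whether any site used the waiver in Parts A to E cannot be determined from the documents.

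Label: wrong as written, low severity. It is a consistency correction with a small safety-baseline consequence.

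**What to change.** Add *Part D Extension only* to both waiver bullets in Section 6.3, in line with Appendix F footnote j. Day -1 hematology, chemistry, coagulation and urinalysis are then required in Parts A to E, as the appendices already say. UPCR and UACR follow the Section 6.3 collection bullet.

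The cost is one phrase in two places. No assessment is added beyond those the protocol already lists, and no analysis changes. If all subjects in Parts A to E had been dosed before the waiver took effect, it is purely a text correction.
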